The proposed research is guided by biobehavioral theories of tobacco regulatory science,^{39,40} psychology,^{15,41} and communication.^{42,43} By using previously tested education messages,⁴⁴ we will determine an optimal combination of message source and presentation type to increase message acceptance and e-cigarette harm perceptions. We will compare the effects of two sources (expert and peer) and two message presentation types (one-sided and two-sided) for young adult vapers and non-vapers. We will use in-lab study for objective assessment of psychophysiological measures (heart rate, skin conductance, and eye-tracking) during message exposure (N=112) to determine optimal messaging. The goal of this study is to determine optimal message source and presentation for young adult vapers and non-vapers to increase message acceptance and harm perceptions using psychophysiology.

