11. PROCEDURES INVOLVED*

After providing informed consent, participants will be randomized to one of four experimental conditions in a 2 (Source: expert and peer) x 2 (Presentation: one-sided and two-sided) design. Data will be collected through iMotions, a psychophysiological data collection platform. We will track participants' eye movements using an eye-tracking device. We will assess heart rate and skin conductance with a sensor by attaching Velcro-strapped electrodes on the fingers of participant's nondominant hand. When the study begins, participants will complete pretest measures, view messages, during which they will be measured on their psychophysiological responses, and complete posttest measures. Messages (see Appendix-A) will be presented in a random order for at least 10 seconds. Between each message segment, a black screen and "get ready" screen will be presented for 10 seconds to return participants' heartrate and skin conductance levels to baseline. This meets the established amount of time (6 seconds) to collect heart rate and skin conductance.⁴⁵ This procedure will be repeated 18 times for the 18 messages. Finally, participants will complete measures on demographics, attitudes, and behavioral intentions. The entire procedure will take approximately 45 minutes. After completion, participants will be thanked and compensated \$50 for participation. Participants will be extensively debriefed about the hypothetical nature of the message source, the health harms of using any tobacco product, and information about the Massachusetts Tobacco Quitline with contact information. We will provide a consent form and verbally reiterate this information.

In order to minimize subject harm as a result of being shocked by static electricity from the sensors, room temperature will remain above 65 degrees when running participants as the colder,

INVESTIGATOR STUDY PLAN - REQUIRED

drier air is more likely to cause static shock. We will also follow all safety guidelines for the equipment. These include having participants wash their hands thoroughly, then use hand sanitizer, and then use an alcohol towelette to clean the finger the sensor will be placed. In addition, participants will be instructed to try to keep their hand still during the study to ensure the sensor does not move.

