All study data are collected using the iMotions 6.4 Biometric Research Platform, a secure, computer-based data collection platform. No self-report or psychophysiological data collected are directly linked to participant identifying information: self-report and psychophysiological data collected through iMotions are tracked using a unique, numeric study identifier that does not contain any personally identifying information. A monitor on the computer will track the participant’s eye movements and three sensors on the participant’s fingers will track heart rate and skin conductance. Each message will appear for ten seconds, which falls above the established amount of time needed (6 seconds) to collect heart rate and skin conductance levels for still messages. This will allow us to take into account baseline levels and time for heart rate and skin conductance to react. After each message, participants will answer the same measures included in the participant survey pertaining to responses toward the message and source, and

INVESTIGATOR STUDY PLAN - REQUIRED

perceived message effectiveness. This process will be repeated 18 times for each of the two message sidedness conditions, resulting in a total of 36 different messages seen by participants. Afterwards, participants will be asked to complete additional measures related to actual message effectiveness (e-cigarette attitudes, risk beliefs, intentions to vape).

Between each message sidedness condition, individuals will see a blank black screen for 10 seconds, then a black screen with the words “get ready” for five seconds followed by another black screen for 10 seconds to return heart rate and skin conductance back to baseline. All methods are consistent with accepted standards of psychophysiological measurement for media studies.

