Cover Page for ClinicalTrials.gov

Document:

Statistical Analysis Plan

Official Study Title:

Responses to Message Source and Presentation Using Psychophysiology

Document Date:

January 17, 2024

Psychophysiological Testing

Study Design and Power Analysis:

We will assess which communication principles influence psychophysiological responses on visual attention, orienting response, and arousal to determine the features that can increase acceptance of e-cigarette education messages in young adults. Eligible participants will be randomly assigned to one of four experimental conditions in a 2 (Source: expert and peer) x 2 (Presentation: one-sided and two-sided) design. For the psychophysiological part of the Aim 1, we will recruit total 112 young adults (age 18 to 24) vapers and susceptible non-vapers. We will use stratified sampling, with n=56 for each vaping status. The estimation was based on Stevens et al.'s (2021) study. Based on simulations as in crowdsourcing study, participants per message condition gave stable ranks for the top 3 messages. We use a conservative approach and propose 7 participants per the message condition for each vaping status. I will use a multi-attribute decision-making (MADM) framework to produce a dataset containing data on participant response to each message with source + presentation type. I will merge crowdsourced and psychophysiological data to rank messages and determine optimal content. This technique has been used in our previous work. MADM provides a practical, transparent framework for considering data across multiple inputs, determining the relative importance of each attribute, and simultaneously evaluating detail at the attribute level and in a summary measure across all attributes using aggregate data.

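### Choosing the optimal source and presentation by ranking aggregate means across conditions, with no participant-level error, will name a winner even when no condition effect exists

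*SAP*

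**What the plan says.** **Assignment.** Protocol section 11 states that "participants will be randomized to one of four experimental conditions", and the SAP agrees: "Eligible participants will be randomly assigned to one of four experimental conditions". Section 11 then has each person view one set of messages: "This procedure will be repeated 18 times for the 18 messages". On this reading the 18 items of a condition are all scored by the same people, and each condition has different people.

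**Analysis.** The SAP's decision framework is to "produce a dataset containing data on participant response to each message with source + presentation type", and then: "I will merge crowdsourced and psychophysiological data to rank messages and determine optimal content". The summary measure uses aggregate data. Protocol section 13 ranks self-report on mean scores, scores heart rate as change from the second before viewing, treats skin conductance similarly, and uses dwell time in milliseconds.

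**Intended conclusion.** Protocol section 5: "we will determine an optimal combination of message source and presentation type".

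**Conflict.** Protocol section 26 describes 18 messages under each of the two sidedness conditions, "resulting in a total of 36 different messages seen by participants". That would make sidedness a within-person factor and leave only source between people.

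**Not stated.** Neither document gives a participant effect, a source or presentation contrast, their interaction, an interval, or a measure of rank uncertainty. Neither says whether ranking is within or across conditions.

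**The concern.** When conditions are formed from different people, the chance average level of those people (generous or harsh raters, strong or weak reactors) enters every item of the condition. Averaging over more messages does not reduce it; only more people do. If items or conditions are then compared across conditions on aggregate means, that shared error looks the same as an effect of source or presentation. This happens with complete data.

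Some condition always comes first, and nothing planned separates that from chance. The SAP justifies its sample size by the stability of the top three ranks, so a top three drawn from a single condition is a result that readers would naturally take as support for that source and presentation.

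**Working it through.** **Step 1. Participants per condition.** The SAP says it will "propose 7 participants per the message condition for each vaping status", with 56 per vaping status and 112 in total.

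- 7 × 4 conditions × 2 statuses = 56, which is not 112.
- 14 × 4 × 2 = 112.
- 7 × 8 × 2 = 112, if the four source directions in Protocol Appendix A are crossed with two presentations.

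I use 4 × 14 as the main case (18 × 4 = 72 items per vaping status) and 8 × 7 as an alternative. The SAP's rank-stability basis cannot be reproduced, because it gives no variance, correlation or simulation settings.

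**Step 2. Shared error.** Model a score as message effect + participant effect (variance ICC) + residual (variance 1 − ICC), so that one response has unit variance about its message effect. The error in an item mean then has two parts:

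- shared by all items of the condition: SD √(ICC/n)
- specific to the item: SD √((1 − ICC)/n)

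With n = 14 and ICC 0.3, the shared part is √(0.3/14) = 0.146 and the item part √(0.7/14) = 0.224. Averaging over 18 messages cuts the item part to √(0.7/(18 × 14)) = 0.053 and leaves 0.146 untouched. At ICC 0.5, with 0.5/14 = 0.0357, the shared error's fraction of between-item variance is:

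- 0.0357/(0.0357 + 0.0357 + 0.15²) = 38% at message SD 0.15
- 0.0357/(0.0357 + 0.0357 + 0.30²) = 22% at message SD 0.30

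**Step 3. Size with no condition effect.** The documents give neither an ICC nor a message SD, so both are assumptions. The table shows the chance that the top three items all come from one condition, over message SD 0.15–0.30 (20,000 simulated trials per setting).

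| ICC | 4 × 14 | 4 × 14, shared error removed | 8 × 7 | 8 × 7, shared error removed |
|---|---|---|---|---|
| 0.05 | 4–7% | 3–5% | 1–2% | about 1% |
| 0.1 | 5–9% | 3–4% | 2–4% | about 1% |
| 0.3 | 12–21% | 3–4% | 8–12% | about 1% |
| 0.5 | 20–32% | 2–4% | 15–23% | about 1% or less |
| 0.7 | 28–44% | 1–3% | 24–37% | under 1% |

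At message SD 0.2 and 4 × 14, one condition holds at least half of the top 18 of 72 items in 1%, 9%, 30% and 50% of trials at ICC 0, 0.1, 0.3 and 0.5. The mean gap between the best and worst condition is 0.13, 0.21, 0.32 and 0.40 SD.

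**Step 4. If Protocol section 26 governs.** Take 28 people per source, each seeing both presentations, message SD 0.2, and no person-specific reaction to sidedness. One condition then holds at least half of the top 18 in 3%, 10% and 17% of trials at ICC 0.1, 0.3 and 0.5. The leading source's share of the top 18 still rises from 57% at ICC 0 to 65% at 0.3 and 69% at 0.5. The leading presentation's share stays at about 56%.

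**Step 5. Participant as the unit.** With no condition effect and 4 × 14, a test on participant means declares a difference in 4–6% of trials at every ICC tried. Treating the 18 responses per person as independent gives 38%, 71% and 84% at ICC 0.1, 0.3 and 0.5. The plan specifies neither test.

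The SD of a participant mean is √(ICC + (1 − ICC)/18), which is 0.582 at ICC 0.3. The difference detectable with 80% power is (1.96 + 0.84) × SD × √(2/n), in SDs of a single response:

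- main effect, 28 v 28 in one vaping status: 0.29, 0.44 and 0.54 at ICC 0.1, 0.3 and 0.5
- two conditions, 14 v 14: 0.41, 0.62 and 0.77

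**The case against.** **The ranking scope is not stated.** A reader might infer one league table of all 72 (or 144) message-by-condition items. The SAP does not say so: its words also fit ranking messages within a condition, and Protocol section 13 speaks of ranking messages and comparing themes. Within one condition the same people score all 18 items, so shared error cannot alter that order. This stands. But within-condition ranking cannot by itself deliver the optimal combination promised in section 5. That needs a comparison across conditions, and aggregate means are all the plan offers.

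**The effect may be small for the physiological outcomes.** Baseline subtraction removes resting heart rate and skin conductance level, so their ICC may be low, and at ICC 0.05–0.1 the excess is a few percentage points. This stands in part. Individual reactivity remains, and self-report means and dwell time have no such correction.

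**The crowdsourced data are merged before ranking.** They may dilute the effect. Their size and design are not given, so the amount is unknown.

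**This is sampling error, not bias.** Correct. Randomisation is not at fault, and a condition contrast carries the same error. The difference is that a contrast reports that error and a ranking hides it.

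**Does shared error also hide the best message?** A reader might infer that removing it would greatly improve the choice of message. It would not. Most of any such gain comes from pooling raters over conditions, and ranking within a single condition finds the best message less often than one combined list. With complete data, centring scores on each participant changes no within-condition rank.

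**Conclusion.** The concern holds for conclusions about source and presentation. If they are drawn by comparing aggregate means across conditions, the plan will name a leader whether or not an effect exists. With no condition effect and 4 × 14, the top three fall in one condition in about 4–9% of trials at ICC 0.05–0.1, rising to 28–44% at ICC 0.7, against about 1–5% without shared error.

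The mechanism follows from the stated design. Its size rests on an assumed ICC and message SD and on laboratory raters alone, and it vanishes as the ICC approaches zero. The documents do not support saying that clustering will happen in most trials, that a single list is specified, or that message ranking within a condition is affected. If each participant sees both sidedness versions, the point applies to source only. The change should be made before analysis, because it alters what the trial can conclude.

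**What to change.** 1. Reconcile Protocol sections 11 and 26 with the SAP on whether a participant sees one or both sidedness versions, and state the number of conditions and participants per condition.
2. State in the SAP that the best source or presentation will not be inferred from a cross-condition ranking of message-by-condition aggregates.
3. Within each vaping status, estimate source, presentation and their interaction from a mixed model with a participant random intercept, or from participant means. Report intervals with the participant as the unit. Adjust for the pretest score where the same measure was taken. If sidedness proves to be within-person, model it as such.
4. Rank the 18 messages separately, on message effects from that model pooled across conditions. Show within-condition ranks if the message-by-condition interaction is material. Carry these results into the multi-attribute step.

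**Cost.** SAP wording and one model per outcome; no new data. The output becomes a message ranking plus condition estimates with wide intervals, not one league table. With 28 v 28 per vaping status, main effects below roughly 0.3–0.5 SD of a single response (ICC 0.1–0.5) will often go undetected, and the report should say so.
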